## 4.3. Lifestyle Guidelines

In this study, male patients who are able to father children and female patients who are of childbearing potential will receive PF-04518600 or PF-04518600 in combination with utomilumab, which is a compound for which the teratogenic risk is currently unknown. Two (2) methods of highly effective contraception must be used throughout the study and continued for 90 days after the last dose. The investigator or his/her designee, in consultation with the patient will confirm the patient has selected two appropriate methods of contraception for the individual patient from the list of permitted contraception methods (see below) and will confirm the patient has been instructed in their consistent and correct use. Patients need to affirm that they meet the criteria for correct use of at least 2 of the selected methods of contraception. The investigator or his or her designee will discuss with the patient the need to use highly effective contraception consistently and correctly according to the Schedule of Activities and document such conversation in the patient's chart. In addition, the investigator or his or her designee will instruct the patient to call immediately if a selected contraception method is discontinued or if pregnancy is known or suspected in the patient or the patient's partner.

Highly effective methods of contraception are those that, alone or in combination, result in a failure rate of less than 1% per year when used consistently and correctly (ie, perfect use) and include the following:

- 1. Established use of oral, inserted, injected (not available in Japan), implanted (not available in Japan) or transdermal hormonal (not available in Japan) methods of contraception is allowed provided the patient plans to remain on the same treatment throughout the entire study and has been using that hormonal contraceptive for an adequate period of time to ensure effectiveness.
- 2. Correctly placed copper-containing intrauterine device (IUD).
- 3. Male condom or female condom used WITH a spermicide (ie, foam, gel, film, cream, or suppository). For countries where spermicide is not available (for example in Japan) or condom plus spermicide is not accepted as highly effective contraception, this option is not appropriate.
- 4. Male sterilization with absence of sperm in the post-vasectomy ejaculate.
- 5. Bilateral tubal ligation or bilateral salpingectomy or bilateral tubal occlusive procedure (provided that occlusion has been confirmed in accordance with the device's label).
- 6. Female partner who meets the criteria for non-childbearing potential, defined as:
  - Have undergone a documented hysterectomy and/or bilateral oophorectomy;
  - Have medically confirmed ovarian failure; or,
  - Achieved postmenopausal status, defined as follows: cessation of regular menses for at least 12 consecutive months with no alternative pathological or physiological cause; status may be confirmed by having a serum follicle-stimulating hormone (FSH) level within the laboratory's reference range for postmenopausal women.

All sexually active male patients must agree to prevent potential transfer of and exposure to drug through semen to their partners by using a condom consistently and correctly, beginning with the first dose of investigational product and continuing for 90 days after the last dose.

### 4.4. Sponsor's Qualified Medical Personnel

The contact information for the sponsor's appropriately qualified medical personnel for the study is documented in the study contact list located in the study coordinator's manual.

To facilitate access to appropriately qualified medical personnel on study-related medical questions or problems, patients are provided with a contact card. The contact card contains, at a minimum, protocol and investigational compound identifiers, patient study numbers, contact information for the investigational site, and contact details for a contact center in the event that the investigational site staff cannot be reached to provide advice on a medical question or problem originating from another healthcare professional not involved in the patient's participation in the study. The contact number can also be used by investigational staff if they are seeking advice on medical questions or problems; however, it should be used

only in the event that the established communication pathways between the investigational site and the study team are not available. It is therefore intended to augment, but not replace, the established communication pathways between the investigational site and the study team for advice on medical questions or problems that may arise during the study. The contact number is not intended for use by the patient directly, and if a patient calls that number, he or she will be directed back to the investigational site.

#### 5. STUDY TREATMENTS

For the purposes of this study, and per International Conference on Harmonization (ICH) guidelines investigational product is defined as a pharmaceutical form of an active ingredient or placebo being tested or used as a reference in a clinical trial, including a product with a marketing authorization when used or assembled (formulated or packaged) in a way different from the approved form, or when used for an unapproved indication, or when used to gain further information about an approved use (ICH E6 1.33). Eligible patients will be enrolled to receive PF-04518600 (and utomilumab for Part B patients) in an open-labeled, unblinded manner. Patients will be registered and successively assigned to the next available treatment slot at a dose level or dose combination level decided on after the previous cohort's safety evaluation and ongoing observations of earlier enrolled patients. For monotherapy, patients will be dosed at 0.01 mg/kg PF-04518600 in the first cohort. For combination therapy, patients will be dosed at 0.1 mg/kg PF-04518600 and 20 mg utomilumab in the first dose combination level. Selected dose for PF-04518600 in the B2 combination therapy dose expansion cohorts is 30 mg (a flat dose equivalent to 0.3 mg/kg) intravenously (IV) Q2W in combination with PF-05082566 20 mg IV every 28 days.

#### 5.1. Allocation to Treatment

Dose level allocation will be performed by the sponsor after patients have given their written informed consent and have completed the necessary baseline assessments. The site staff will e-mail a complete registration form to the designated sponsor study team member. The sponsor will assign a patient identification number, which will be used on all Case Report Form (CRF) pages and other study-related documentation or correspondence referencing that patient and e-mail to the site.

No patient shall receive investigational product until the investigator or designee has received the following information in writing from the sponsor:

- Confirmation of the patient's enrollment.
- Specification of the dose level for that patient; and
- Permission to proceed with dosing the patient.

The sponsor or designee will notify the other sites of the inclusion of a new patient, and will inform study sites about the next possible enrollment date.

## **5.2. Patient Compliance**

The site will complete required dosage Preparation Record located in the study manual. The use of the Preparation Record is preferred but it does not preclude the use of an existing appropriate clinical site documentation system. The existing clinical site's documentation system should capture all pertinent/required information on the preparation and administration of the dose. This may be used in place of the Preparation Record after approval from the Pfizer monitor.

At each study visit, the Investigator, or designee, will assess the patient's compliance with the study requirements. The assessment will include checks of protocol compliance and concomitant mediation use.

## 5.3. Investigational Product Supplies

PF-04518600 and utomilumab will be supplied for the study by Pfizer. No patients or third-party payers will be charged for investigational product.

Study centers will receive a supply of Clinical Trial Material upon activation with instructions on how to confirm drug receipt. Resupplies will be made during the course of the study based on need. The details on drug supply will be provided in the Study Manual. The study monitor should be contacted for any issues related to drug supplies.

# 5.3.1. Dosage Forms and Packaging

#### 5.3.1.1. PF-04518600

PF-04518600 10 mg/mL injection is presented as a sterile solution for intravenous administration. Each vial contains 108 mg of PF-04518600 in 10.8 mL of aqueous buffered solution, with a nominal volume of 10 mL, is sealed with a coated stopper and an overseal, and labeled according to local regulatory requirements. The vial is designed for single use.

PF-04518600 will be shipped under refrigerated conditions (2-8°C) and should be stored under refrigerated conditions (2-8°C).

#### **5.3.1.2.** Utomilumab

Utomilumab drug product will be supplied in glass vials at a 10 mg/mL concentration and labeled as open supplies. Each vial is packed in an individual carton.

#### 5.3.2. Preparation and Dispensing

See the investigational product (IP) Manual located in the Study Manual for instructions on how to prepare the investigational product for administration. Investigational product should be prepared and dispensed by an appropriately qualified and experienced member of the study staff (eg, physician, nurse, physician's assistant, practitioner, pharmacist, or medical assistant) as allowed by local, state, and institutional guidance. Only qualified personnel who are familiar with procedures that minimize undue exposure to them and to the environment should undertake the preparation, handling, and safe disposal of biologic agents.

#### 5.4. Administration

## 5.4.1. Part A1 Monotherapy

PF-04518600 will be administered intravenously with adjustment for body weight at every cycle. A cycle is defined as the time from Day 1 dose to the next Day 1 dose. If there are no treatment delays, a cycle will be 2 weeks in duration. PF-04518600 will be administered on Day 1 of each 2 week cycle per the IP Manual as an intravenous (IV) infusion over 60 minutes (-5 to +15 minutes and should include the time needed to flush the infusion line) on an outpatient basis. If infusion reaction occurs, infusion rate maybe reduced (refer to Section 5.4.5.1 Infusion Reactions and Appendix 4 for management of infusion reactions).

The use of an infusion pump is the preferred method of administration to ensure accurate delivery of the investigational product, but gravity drips are allowed.

Each patient may receive PF-04518600 until disease progression by irRECIST (see Section 5.4.6 Treatment After Initial Evidence of Radiological Progression), patient refusal, or unacceptable toxicity occurs, or end of study, whichever occurs first.

The dose level will be assigned by the sponsor (Section 5.1 Allocation to Treatment). Patient actual body weight will be used to calculate the mg/kg dose, and the calculated dose will be rounded off to the second decimal point. All patients should be weighed within 72 hours prior to dosing for every cycle to ensure they did not experience either a weight loss or gain >10% from the prior weight used to calculate the amount of PF-04518600 required for dose preparation. Decision to recalculate PF-04518600 dose based on the weight obtained at each cycle can be in accordance with institutional practice, however if the patient experienced either a weight loss or gain >10% compared to the weight used to calculate the initial dose, the amount of PF-04518600 required for investigational product preparation and administration for the current cycle must be recalculated using this most recent weight obtained.

# 5.4.2. Part A2 Monotherapy

PF-04518600 will be administered intravenously as a flat dose. A cycle is defined as the time from current Day 1 dose to the next Day 1 dose. If there are no treatment delays, a cycle will be 2 weeks in duration. PF-04518600 will be administered on Day 1 of each 2 week cycle per the IP Manual as an intravenous (IV) infusion over 60 minutes (-5 to +15 minutes and should include the time needed to flush the infusion line) on an outpatient basis. If infusion reaction occurs, infusion rate maybe reduced (refer to Section 5.4.5.1 Infusion Reactions and Appendix 4 for management of infusion reactions).

The use of an infusion pump is the preferred method of administration to ensure accurate delivery of the investigational product, but gravity drips are allowed. Please refer to the IP manual for infusion rate and duration.

Each patient may receive PF-04518600 until disease progression by irRECIST (see Section 5.4.6 Treatment After Initial Evidence of Radiological Progression), intolerability, death, or until end of study, whichever comes first.

The dose level will be assigned by the sponsor (Section 5.1 Allocation to Treatment).

# 5.4.3. Part B1 Combination Therapy

In Part B1, utomilumab will be administered on Day 1 of every other cycle (every 28 days) per IP Manual as an intravenous (IV) infusion over 60 minutes (-5 to +15 minutes and should include the time needed to flush the infusion line). Utomilumab will be administrated intravenously using a flat dose.

Per monotherapy, PF-04518600 will be administered on Day 1 of each 2 week cycle per the IP Manual as an intravenous (IV) infusion over 60 minutes (-5 to +15 minutes and should include the time needed to flush the infusion line) on an outpatient basis. PF-04518600 will be administered intravenously with adjustment for body weight at every cycle. On cycles whereby both PF-04518600 and utomilumab are to be administered on the same day, PF-04518600 will be administered after, but no sooner than 30 minutes after completion of the utomilumab infusion in absence of infusion reaction and after post-utomilumab and pre-PF-04518600 pharmacokinetic blood draws (see Section 5.4.5.6.2 Dose Reductions, Interruptions, and Discontinuation Criteria Part B Combination). All blood draws should be taken from the contra-lateral arm of the infusion. Furthermore, separate infusion bags, infusion lines, and filters must be used for each investigational product. Indwelling catheters should be flushed prior to infusion of each investigational product.

A cycle is defined as the time from Day 1 dose of PF-04518600 to the next Day 1 dose. If there are no treatment delays, a cycle will be 2 weeks. Each patient may receive PF-04518600 and utomilumab until disease progression by irRECIST (see Section 5.4.6 Treatment After Initial Evidence of Radiological Progression), intolerability, death, or until end of study, whichever comes first.

If infusion reaction occurs, refer to Section 5.4.5.1 Infusion Reactions and Appendix 4 for management of infusion reactions. If premedication is required for the management of infusion reactions, administration of PF-04518600 not sooner than 30 minutes before utomilumab administration may be considered.

#### 5.4.4. Part B2 Combination Therapy

In Part B2, utomilumab will be administered on Day 1 of every other cycle (every 28 days) per IP Manual as an intravenous (IV) infusion over 60 minutes (-5 to +15 minutes and should include the time needed to flush the infusion line). Utomilumab will be administrated intravenously using a flat dose.

PF-04518600 will be administered intravenously as a flat dose on Day 1 of each 2 week cycle per the IP Manual as an intravenous (IV) infusion over 60 minutes (-5 to +15 minutes and should include the time needed to flush the infusion line). On cycles whereby both PF-04518600 and utomilumab are to be administered on the same day, PF-04518600 will be administered after, but no sooner than 30 minutes after completion of the utomilumab infusion in absence of infusion reaction and after post-utomilumab and pre- PF-04518600 pharmacokinetic blood draws (see Section 5.4.5.6.2 Dose Reductions, Interruptions, and Discontinuation Criteria Part B Combination). All blood draws should be

taken from the contra-lateral arm of the infusion. Furthermore, separate infusion bags, infusion lines, and filters must be used for each investigational product. Indwelling catheters should be flushed prior to infusion of each investigational product.

A cycle is defined as the time from Day 1 dose of PF-04518600 to the next Day 1 dose. If there are no treatment delays, a cycle will be 2 weeks. Each patient may receive PF-04518600 and utomilumab until disease progression by irRECIST (see Section 5.4.6 Treatment After Initial Evidence of Radiological Progression), intolerability, death, or until end of study, whichever comes first.

If infusion reaction occurs, refer to Section 5.4.5.1 Infusion Reactions and Appendix 4 for management of infusion reactions. If premedication is required for the management of infusion reactions, administration of PF-04518600 not sooner than 30 minutes before utomilumab administration may be considered.

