#### **Part B Combination Therapy:**

Part B1 Combination Therapy Dose Escalation.

Part B1, the combination therapy dose escalation phase, will enroll approximately 55 patients. At least 6 patients must have been evaluated for the 28 day DLT observation period at the 0.3 mg/kg dose level in Part A1 PF-04518600 (OX40 agonist) monotherapy before Part B1 can be initiated. Part B1 will study sequential dose levels of PF-04518600 (0.1, 0.3, 1.0 and 3 mg/kg with an option of 10 mg/kg pending data from Part A1) combined with either 20 mg or 100 mg of utomilumab (4-1BB agonist) in adult patients with non-small cell lung cancer (NSCLC), HNSCC, melanoma, bladder, gastric or cervical cancer who are unresponsive to currently available therapies or for whom no standard therapy is available. The starting dose level will be 0.1 mg/kg of PF-04518600 and 20 mg of utomilumab, given no sooner than 30 minutes apart (for dosing schedule, please see Section 5.4.3 Administration Part B Combination Therapy). Based on emerging data in the 10 mg/kg Part A1 cohort, an optional cohort of 10 mg/kg PF-04518600 in combination with 100 mg of utomilumab may be evaluated.

A mTPI method, targeting a DLT rate of 25% and an acceptable DLT interval (20%-30%), will be utilized for dose escalation (see Section 3.1.5 Criteria for Dose Escalation). If peripheral blood samples indicate preliminary signs of immune modulation in the first 2-4 patients, the dose level will be expanded for pharmacodynamic evaluation; these additional patients will undergo mandatory pre-treatment and on treatment biopsies. In case of intolerable toxicity at the starting dose level, the dose combination will be reduced to

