- 19. Utomilumab Treatment: utomilumab will be administered once every 28 days as an IV infusion over 60 minutes (-5 to +15 minutes) and should include the time needed to flush the infusion line. Day 1 safety labs (blood chemistry, hematology, coagulation, and urinalysis) need to be reviewed by a physician prior to dosing at the beginning of each cycle. On cycles whereby both PF-04518600 and utomilumab are to be administered on the same day, PF-04518600 will be administered no sooner than 30 minutes after completion of the utomilumab infusion and after post- utomilumab and pre- PF-04518600 pharmacokinetic blood draws. Furthermore, separate infusion bags and filters must be used for each investigational product. Treatment with investigational product will continue until disease progression by irRECIST, patient refusal, unacceptable toxicity occurs, or the end of the study, whichever occurs first.
- 20. PF-04518600 Treatment: PF-04518600 will be administered once every 2 weeks as an IV infusion over 60 minutes (-5 to +15 minutes) and should include the time needed to flush the infusion line. Utomilumab will be administered first, and PF-04518600 will be administered no sooner than 30 minutes after completion of utomilumab infusion and after post- utomilumab and pre- PF-04518600 pharmacokinetic blood draws. Day 1 safety labs (blood chemistry, hematology and urinalysis) need to be reviewed by a physician prior to dosing at the beginning of each cycle. Treatment with investigational product will continue until disease progression by irRECIST, patient refusal, unacceptable toxicity occurs, or the end of the study, whichever occurs first.

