A maximum of approximately 210 patients are expected to be enrolled into the study. Patients will complete up to 4 weeks of screening. Patients in Parts A1 and B1 who are part of the expansion of any dose level and all patients in Parts A2 and B2 will undergo mandatory pre- and on-treatment biopsies. If the Investigator judges the risk of certain on-treatment biopsies unacceptable for the patient (eg, based on site of tumor, potential for complications during/after procedure, etc.) the medical monitor must be consulted (see Section 1.4 Rationale for Pre Treatment and On Treatment Biopsies). Patients will receive doses of PF-04518600 intravenously (IV) over 60 minutes (-5 to +15 minutes) every 2 weeks. Patients in Part B will also receive doses of utomilumab intravenously (IV) over 60 minutes (-5 to +15 minutes) every 28 days. Following the initial dose, treatment with investigational product will continue until disease progression by irRECIST (see Section 0 Treatment after Initial Evidence of Radiological Disease Progression), patient refusal, unacceptable toxicity occurs, or the end of the study, whichever comes first. Patients will be allowed to stay on study, if the treating physician feels that it is in the patient's best interest, in the case of radiological progression and in the absence of clear clinical progression. A follow-up visit after approximately 4 weeks after the last dose for AE and SAE collection will be conducted. Assessment of late immune related responses will be evaluated up to 98 days after the first dose of Cycle 1. Because atypical tumor responses after growth of pre-existing lesions or appearance of new lesions have been observed with immune checkpoint inhibitors, study B0601002 will assess tumor response based on both response evaluation criteria in solid tumor (RECIST) and Immune-related Response Criteria Derived from RECIST v1.1 (irRECIST). Survival data will be collected (by phone, every 8 weeks, see Section 6.3 Follow-up Visit, Section 7.4 Tumor Response Assessments and Appendix 5). 85-87 The time on study can vary depending on the observed toxicity and potential benefit an individual patient derives. It is estimated that patients will remain on treatment for approximately 12-18 weeks, making total study duration approximately 20-26 weeks (exclusive of 2-year survival follow-up). Actual duration can be longer, if a patient derives benefit from study treatment. However, 2 years from the time of the first dose of investigational product of the last patient enrolled or last surviving patient (whichever is later) the study will be closed.

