## 5.4.5.1. Infusion Reactions

Following the first infusion of some monoclonal antibody therapeutics, some patients experience fever, headache, nausea, vomiting or hypotension. These adverse events (AEs) are generally ascribed to lysis of cellular targets, cytokine release, or complement activation.

In the case of infusion reaction, characterized by fever and chills, and less commonly hypotension, either experienced by a particular patient or if seen in other patients, pretreatment medication should be administered to reduce the incidence and severity. A regimen is suggested here; however, if local standard of care is a different regimen, this will be allowed. In cases of infusion reactions, patients should be pretreated with acetaminophen and diphenhydramine (or other antihistamine) approximately 0.5 to 2 hours before investigational product administration. The pretreatment medications will not be supplied by Pfizer. Suggested starting doses are 650 to 1000 mg acetaminophen and 50 mg

diphenhydramine (or equivalent for other antihistamines) either IV or oral. Two (2) additional doses of acetaminophen may be administered approximately every 4-6 hours after the initial pretreatment or as needed.

#### **5.4.5.2.** Hypersensitivity Types 1 and 3

Type 1 hypersensitivity or allergic (eg, shortness of breath, urticaria, anaphylaxis, angioedema) reactions are theoretically possible in response to any injected protein. Immune complex mediated Type 3 hypersensitivity reactions are similar to the adverse events (AEs) of Type 1 reactions but are likely to be delayed from the time of infusion and may include symptoms such as rash, urticaria, polyarthritis, myalgias, polysynovitis, fever, and, if severe, glomerulonephritis.

All patients should be closely observed while receiving investigational product infusions and monitoring for clinical signs of a systemic reaction will continue thereafter for clinical signs of allergic reactions/hypersensitivity.

In the case of a hypersensitivity reaction, the patient will be treated symptomatically with supportive care, further monitoring, and treatment with anti-histamines and/or corticosteroids. Study infusions may be stopped and the patient will be followed until the end of the study.

Detailed guidance on treatment, dose interruptions and potential retreatment is provided in Appendix 4.

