# 5.4.5.6.2. Part B Combination Therapy

Intrapatient dose reductions are not permitted during the combination therapy with PF-04518600 and utomilumab unless, in discussion with the sponsor, a dose combination level is deemed to be above the determined MTD for the combination.

Given the expected similarities of side effect profile and mechanism between the two co-stimulation monoclonal antibodies, both treatments must be interrupted or discontinued together. Patients will not be permitted to continue treatment with one agent, while the other agent is either interrupted or permanently discontinued. If infusion related reactions are observed following the administration of the first agent, administration of the second agent will be withheld until symptoms resolve (see Section 5.4.5.1 Infusion Reactions).

Treatment of irAEs should follow guidelines set forth in Table 4 in Section 5.4.5.4 Recommended dose modifications for any other drug-related toxicity are illustrated in Table 6.

Table 6. Treatment Interruptions/ Discontinuations for Drug Related Toxicity at Start of Subsequent Cycle

Toxicity	NCI CTCAE Severity Grade	Treatment Modifications
Hematologic abnormalities.	Grade 3	
 
Withhold until recovery to Grade 1 or better.
 
If toxicity does not resolve to Grade 1 or better within 4 weeks of last infusion, consider permanent discontinuation after consultation with the sponsor.
 
Upon the second occurrence of the same Grade 3 toxicity that does not resolve to Grade ≤1 by the next administration, treatment must be permanently discontinued.
 

	Grade 4	Permanent discontinuation.     Exceptions are:     Single laboratory values out of normal range that are unlikely related to investigational product (s) as assessed by the Investigator, do not have any clinical correlate, and resolve within 7 days with adequate medical management.
Infusion-related reaction.	Grade 1-4	• See Section 5.4.5.1 and Appendix 4.
Hypersensitivity reaction.	Grade 1-4	• See Section 5.4.5.2 and Appendix 4.

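### The premedication exception in Protocol 5.4.3 and 5.4.4 makes 30 minutes the longest gap between the two antibodies; every other statement makes it the shortest

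*Protocol*

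**What the plan says.** Protocol 5.4.4 (Part B2) gives the default for days when both antibodies are due: "PF-04518600 will be administered after, but no sooner than 30 minutes after completion of the utomilumab infusion in absence of infusion reaction". Section 5.4.3 gives the same rule for Part B1. Footnote 20 of the Part B1 schedule fixes both the order and the interval: "Utomilumab will be administered first, and PF-04518600 will be administered no sooner than 30 minutes after completion of utomilumab infusion". Footnote 19 of that schedule and footnote 20 of the A2/B2 schedule give the same interval: "PF-04518600 will be administered no sooner than 30 minutes after completion of the utomilumab infusion". The Protocol Summary, Section 3.1.2.1 and SAP 2.1 describe the Part B1 starting dose level without naming an order: "given no sooner than 30 minutes apart".

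The last sentence of 5.4.3 and of 5.4.4 then allows the order to be reversed when premedication is needed for infusion reactions: "administration of PF-04518600 not sooner than 30 minutes before utomilumab administration may be considered".

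Section 5.4.5.6.2 governs reactions between the two doses: "If infusion related reactions are observed following the administration of the first agent, administration of the second agent will be withheld until symptoms resolve".

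**The concern.** A limit on how soon something may happen works in opposite directions before and after the reference event. Not sooner than 30 minutes *after* an event sets a minimum wait. Not sooner than 30 minutes *before* an event sets a maximum lead. The exception appears to carry over the default phrasing with the order reversed, and this turns the bound round. It also drops the reference to completion of the infusion, so it is unclear whether the clock runs from the start or the end of PF-04518600.

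The rule in 5.4.5.6.2 needs time for a reaction to the first antibody to show itself. The exception, as worded, removes the guaranteed 30 minutes in patients already being managed for infusion reactions. It also makes it harder to tell which antibody caused a reaction. Permitting the reversed order is not itself in question.

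**Working it through.** No sample size, power or error rate is involved. The check is to classify every statement of the interval and then see what the exception literally permits.

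**Statements other than the exception**

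| Place | Measured from | Bound |
|---|---|---|
| Protocol Summary, Part B1 | not specified, either order | at least 30 min |
| Part B1 schedule, footnote 19 | completion of utomilumab | at least 30 min |
| Part B1 schedule, footnote 20 | completion of utomilumab | at least 30 min |
| A2/B2 schedule, footnote 20 | completion of utomilumab | at least 30 min |
| Protocol 3.1.2.1 | not specified, either order | at least 30 min |
| Protocol 5.4.3, default rule | completion of utomilumab | at least 30 min |
| Protocol 5.4.4, default rule | completion of utomilumab | at least 30 min |
| SAP 2.1, Part B1 | not specified, either order | at least 30 min |

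That is 8 statements, 7 in the protocol and 1 in the SAP: 5 run from completion of utomilumab and 3 are neutral as to order. All 8 set a minimum.

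**The exception (2 sentences, in 5.4.3 and 5.4.4)**

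Let T be the start of utomilumab. Not sooner than 30 minutes before T means PF-04518600 time ≥ T − 30. Section 5.4.4 gives the PF-04518600 infusion as 60 minutes (−5 to +15), so its duration d is 55 to 75 minutes.

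- If administration means the *end* of PF-04518600, end ≥ T − 30, so the gap is at most 30 minutes and can be 0.
- If it means the *start*, end = start + d ≥ T − 30 + d. With d = 55 this is T + 25, with d = 60 it is T + 30, and with d = 75 it is T + 45. PF-04518600 would still be running at least 25 to 45 minutes into the utomilumab infusion.

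Neither reading agrees with the eight statements above.

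**How often it could arise**

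Utomilumab is given every 28 days, and Section 3.1 gives the expected duration: "It is estimated that patients will remain on treatment for approximately 12-18 weeks".

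- 12 weeks: doses at weeks 0, 4 and 8, so 3 same-day dosings.
- 18 weeks: doses at weeks 0, 4, 8, 12 and 16, so 5 same-day dosings.

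This is a ceiling, because the exception needs a premedication trigger. Where the trigger is the patient's own reaction, the first dosing does not qualify.

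**The case against.** **Scope.** Six of the eight comparison statements concern Part B1, and the three that are neutral as to order are one sentence repeated. For Part B2 only footnote 20 of the A2/B2 schedule and the default rule in 5.4.4 apply. Both cover only utomilumab-first dosing, and the latter is qualified by the absence of a reaction. This is true, but it means that the exception sentence is the only B2 text setting an interval for the reversed order, so its wording matters more there.

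**A deliberate cap.** Section 5.4.5.1 places premedication about 0.5 to 2 hours before dosing. With premedication 30 minutes before PF-04518600, a 60-minute infusion and a gap of at most 30 minutes, utomilumab starts no later than 30 + 60 + 30 = 120 minutes after premedication, within the 2 hours. The cap could therefore be meant to let one premedication cover both antibodies. The documents do not say so, and the default order already puts the second antibody at 30 + 60 + 30 = 120 minutes or later. Nor does the cap keep utomilumab inside the window in general: with premedication 2 hours ahead, even a zero gap gives 120 + 60 = 180 minutes. The corrected wording gives the same 120-minute minimum as the default (30 + 75 + 30 = 135 minutes with the longest permitted infusion). The window is approximate, and repeat acetaminophen is allowed.

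**Existing safeguards.** The withholding rule in 5.4.5.6.2 applies in either order. Section 5.4.5.2 requires close observation during infusions, after which "monitoring for clinical signs of a systemic reaction will continue thereafter". Appendix 4 halves the rate after a Grade 2 reaction, stops treatment after a second reaction at the reduced rate, and discontinues it after Grade 3 or 4. This stands and limits the harm. It does not restore a minimum gap.

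**Conclusion.** The exception is wrong as written. The shortest permitted gap is 30 minutes in eight statements. In the two exception sentences it is zero on the completion-based reading, and the infusions overlap on the start-based one. No text in either document explains or overrides the difference.

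The intent, at least 30 minutes, is inferred from the other statements rather than stated. The investigational product manual, to which both sections refer, was not available and may say more.

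This is a minor point. The exception is optional and conditional, and no endpoint, sample size or error rate is affected. Section 3.1.2.2 shows that Part B1 results have already fixed the B2 dose, so the correction matters mainly for 5.4.4.

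**What to change.** Replace the last sentence of 5.4.3 and of 5.4.4 with wording such as: *When premedication is needed because of infusion reactions, PF-04518600 may be given first; utomilumab must then start at least 30 minutes after the PF-04518600 infusion has finished.* Add a cross-reference to this exception in footnotes 19 and 20 of the Part B1 schedule and footnote 20 of the A2/B2 schedule, none of which mentions it.

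The gap is then at least 30 minutes in either order. With PF-04518600 first, start-to-start spacing is at least 60 + 30 = 90 minutes at the nominal duration (85 to 105 minutes for infusions of 55 to 75 minutes).

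The cost is one sentence in two sections and a cross-reference in three footnotes, with no new data, visits or analyses. If a cap really was intended, the sponsor should state it and the reason, and say whether it runs from the start or the end of the infusion.
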